9.1.4. AESI (adverse events of special interest)

An adverse event of special interest (AESI), serious or non-serious, is one of scientific and medical concern specific to the sponsor's product, for which ongoing monitoring and rapid communication (≤ 48 hours) by the investigator to the sponsor can be appropriate. Such an event might warrant further investigation in order to characterize and understand it. Depending on the nature of the event, rapid communication by the trial sponsor to other parties (e.g. regulators) might also be warranted (adapted from CIOMS 2005).

In case of the CoVac-1 vaccine in this study, AESIs include proven SARS-CoV-2 infection and potential immune mediated diseases (pIMDs, see Appendix 14.6)¹¹⁷. Instructions for management are provided in section 6.3.

With regard to trial schedule and AESI occurrence, AESIs constitute:

- Novel proven (PCR-based) SARS-CoV-2 infection accompanied by symptoms
- Novel proven (PCR-based) SARS-CoV-2 positivity without symptoms
- Novel potential immune mediated diseases (pIMD) according the listed diseases in Appendix 14.6
- Formation of granuloma at the injection site

AESIs are always to be addressed as part of the patient safety report to the DSMB (section 1.4), also non-occurrence will be mentioned. Depending on the decision of DSMB, the vaccination of further volunteers will be permanently stopped.

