2.1.1. Primary Endpoint

The nature, frequency, and severity of AEs and/or SAEs associated with administration of CoVac-1:

- Solicited: ADRs/AEs occurring from the time of each injection throughout 28 days following the procedure, facilitated by use of a volunteer diary
- Unsolicited: AEs from the time of injection throughout 56 days following injection
- SAEs from the time of injection until the final study visit for each subject
- Incidence of AESIs until the final study visit for each subject

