15. Known hypersensitivity to any of the components included in the CoVac-1 vaccine

16. Pre-existing auto-immune disease except for Hashimoto thyroiditis and mild (not requiring immunosuppressive treatment) psoriasis

Protocol		
Protocol code and Short Title:	P-pVAC-SARS-CoV-2	Date/Version:08.03.2021/V1.4

5. General Information on the Investigational Medical Product (IMP)

Definition of terms

Drug substances:	Six SARS-CoV-2-derived HLA class II peptides derived and the TLR1/2 ligand XS15
Peptide cocktail:	Peptide cocktail for each study volunteer including 6 immunogenic SARS-CoV-2 peptides and the TLR1/2 ligand XS15
IMP/Drug product/peptide vaccine:	CoVac-1: Peptide cocktail emulsified in Montanide ISA 51 VG
IMP administration:	subcutaneous injection with 2ml syringe (e.g. BD Emerald) and needle (e.g. BD Eclipse Needle 27Gx1/2)

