The TLR 1/2 ligand XS15 will be administered subcutaneously together with the SARS-CoV-2 specific peptides emulsified in Montanide ISA 51 VG. XS15 was never used in a clinical trial before. Common side effects of other TLR ligands used for peptide vaccination are reported to be usually mild, comprising local skin reactions, fatigue, flu-like symptoms like fever, muscular pain and aigue. TLR ligands can worsen pre-existing autoinflammatory skin disorders.

Previous application of XS15 in a healthy volunteer and cancer patients (within the scope of individual healing attempts) did, besides local reactions at the vaccination site including formation of granuloma, not cause relevant systemic side effects, in particular no allergic or anaphylactic reactions. More detailed information on XS15 is provided with the current IB (1.0. 27 May 2020).

5.7.2.3. *Side effects of Montanide ISA 51 VG*

Montanide ISA51 is an oil adjuvant suitable for human injection that will be administered together with the SARS-CoV-2 specific peptides and XS15 subcutaneously. Montanide ISA 51 VG was used as an adjuvant in more than 100 peptide vaccination. Most common side effects

Protocol		
Protocol code and Short Title:	P-pVAC-SARS-CoV-2	Date/Version:08.03.2021/V1.4

are injection site reaction (68%) including granuloma development, fatigue (54%), fever (41%), gastrointestinal disorders (32%) and injection site or local erythema (28%)⁸⁹. In general, the observed AEs from controlled trials involving non-healthy as well as healthy individuals were mild to moderate in intensity. Further side effects rarely reported were erythema nodosum (2/36 patients, 5%)¹¹³ and the development of sterile abscesses at injection site (10%)⁸⁹⁻⁹¹.

More detailed information on Montanide ISA 51 VG is provided with the current IB (Version 3291/GB/03/June 2019).

6. Study Procedures and Examination Method

This study will consist of the following consecutive phases: Study entry, vaccination/treatment and follow-up. Time-points and trial procedures are listed in Table 1.

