9.1. Definition of Adverse Events and Side Effects

9.1.1. Adverse Events

Any untoward clinical relevant medical occurrence in a volunteer or clinical investigation subject to whom a pharmaceutical product had been administered and which does not necessarily have a causal relationship with this treatment. An AE can therefore be any clinical relevant unfavorable and unintended sign (including an abnormal laboratory finding), clinical relevant symptom, or disease temporally associated with the use of a medicinal (investigational) product, whether or not related to the medicinal (investigational) product.

An AE may be:

- New clinical relevant symptoms/ medical conditions
- New clinical relevant diagnosis
- Clinical relevant changes of laboratory parameters
- Diseases and medical consequences of an accident
- Worsening of medical conditions/ diseases existing before clinical trial start
- Recurrence of disease
- Clinical relevant increase of frequency or intensity of episodical diseases

A pre-existing disease or symptom will not be considered an AE unless there will be an untoward change in its intensity, frequency or quality. This change will be documented by the investigator.

In general, abnormal laboratory findings or clinical events without clinical significance (based on the investigator's judgement) should not be recorded as AEs.

Surgical procedures themselves are not AEs; they are therapeutic measures for conditions that require surgery. The condition for which the surgery is required may be an AE. Planned surgical measures permitted by the clinical trial protocol and the condition(s) leading to these measures are not AEs, if the condition leading to the measure was present prior to inclusion into the trial.

AEs are classified as "non-serious" or "serious".

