14.6. List of specific immune mediated diseases (pIMDs)

Neuroinflammatory disorders	Musculoskeletal disorders	Skin disorders	Liver disorder	Gastrointestinal disorders	Metabolic & endocrine disorders	Vasculitides	Others
Cranial nerve inflammatory disorders, including paryses/paresis (e.g., Bell's palsy)	Systemic lupus erythematosus	Psoriasis	Autoimmune hepatitis	Crohn's disease	Autoimmune thyroiditis (including Hashimoto thyroiditis)	Large vessels vasculitis including: giant cell arteritis such as Takayasu's arteritis & temporal arteritis	Autoimmune haemolytic anaemia
Acute disseminated encephalomyelitis including site-specific variants: encephalitis, encephalomyelitis, myelitis, myeloradiculoneuritis, cerebellitis	Systemic sclerosis (with limited or diffuse cutaneous involvement)	Vitiligo	Primary biliary cirrhosis	Ulcerative colitis	Grave's or Basedow's disease		Autoimmune thrombocytopenia
Multiple sclerosis	Dermatomyositis	Erythema nodosum	Primary sclerosing cholangitis	Ulcerative proctitis	Diabetes mellitus type I		Antiphospholipid syndrome
Transverse myelitis	Polymyositis		Autoimmune cholangitis.	Celiac disease	Addison's disease		Pernicious anaemia
Optic neuritis	Anti-synthetase syndrome	Cutaneous lupus erythematosus					Raynaud's phenomenon
Narcolepsy	Rheumatoid arthritis	Alopecia areata					Uveitis
	Juvenile chronic arthritis (including Still's disease)	Lichen planus					Autoimmune myocarditis/cardiomyopathy
	Polymyalgia rheumatica	Sweet's syndrome					Sarcoidosis
	Psoriatic arthropathy	Morphea					Stevens-Johnson syndrome
	Relapsing polychondritis						Sjögren's syndrome
Myasthenia gravis (including Lambert-Eaton myasthenic syndrome)	Mixed connective tissue disorder						Idiopathic pulmonary fibrosis
							Goodpasture syndrome

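### The AESI definition counts only novel immune-mediated disease, so a flare of the psoriasis or Hashimoto thyroiditis that the trial admits stays off the pIMD line

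*Supplement*

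**What the plan says.** All references are to protocol V1.4 (8 March 2021).

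- **Eligibility (4.1.2, no. 16).** The exclusion reads "Pre-existing auto-immune disease except for Hashimoto thyroiditis and mild (not requiring immunosuppressive treatment) psoriasis". It applies to both parts.
- **Adjuvant warning (5.7.2.2, side effects of XS15).** "TLR ligands can worsen pre-existing autoinflammatory skin disorders". XS15 is a TLR1/2 ligand.
- **List of pIMDs (Appendix 14.6).** Psoriasis stands under skin disorders, and "Autoimmune thyroiditis (including Hashimoto thyroiditis") under metabolic and endocrine disorders.
- **AESI definition (9.1.4).** The lead-in says that "AESIs include proven SARS-CoV-2 infection and potential immune mediated diseases (pIMDs, see Appendix 14.6"), with no restriction to new disease. The itemised list that follows is narrower: "Novel potential immune mediated diseases (pIMD) according the listed diseases in Appendix 14.6". It has no item for exacerbation. Granuloma at the injection site is a separate item.
- **Primary endpoint (2.1.1).** Two of its components are "Incidence of AESIs until the final study visit for each subject" and "Unsolicited: AEs from the time of injection throughout 56 days following injection". SAEs are counted to the final visit.
- **AE definition (9.1.1).** An AE may be "Worsening of medical conditions/ diseases existing before clinical trial start".

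**The concern.** The protocol lets in people who already have a listed immune-mediated disease and says that the adjuvant class can aggravate one kind of it. It then words the category built for immune-mediated harm so that such aggravation does not qualify. For an admitted volunteer's own disease, the pIMD count is zero by definition, whatever happens after vaccination.

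Two things are at stake. The first is labelling. Section 9.1.4 requires AESIs to be addressed in the safety report to the DSMB, including a statement when none occurred. That statement could truthfully say that no pIMD occurred while a psoriasis flare sits in the general AE listing. The second is time. AESIs are counted to month 6 and unsolicited AEs to day 56, so the label decides whether a late, non-serious flare is counted at all.

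**Working it through.** **Where an event lands.** Reading 2.1.1, 9.1.1, 9.1.4 and 9.2 together:

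| Event in a vaccinated volunteer | Unsolicited AE (to day 56) | SAE (to final visit) | pIMD as AESI (to final visit) |
|---|---|---|---|
| New onset of a listed disease | yes, to day 56 | if serious | yes |
| Non-serious flare of an admitted disease, onset by day 56 | yes | no | no |
| Serious flare of an admitted disease | yes, to day 56 | yes | no |
| Non-serious flare, onset between day 56 and month 6 | no | no | no |

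**The last row.** Section 9.2 ends AE collection at Visit 5 (day 56). Table 1 marks AE assessment at V6-7 as well, but its footnote 11 sets follow-up at 56 days or until drug-related toxicities resolve, whichever is later, and 6.2.6 lists only medical history, T-cell and serology samples for those visits. Section 6.2.8 records medically attended AEs at unscheduled contacts. A late flare may therefore be recorded, but 2.1.1 gives a non-serious one no component to count in.

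**Size of one event.** On the pIMD line, 1/36 = 2.8% of all volunteers, or 1/24 = 4.2% of Part II.

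**Any-AESI incidence.** Section 5.7.2.1 reports granuloma in 100% of the 12 Part I volunteers. Any-AESI incidence there is 12/12 with or without a flare, so only a separate pIMD line can show the signal.

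**Number affected.** The documents do not give it. Purely as an assumption, let 5% to 15% carry one of the two conditions: 0.05 × 36 = 1.8 to 0.15 × 36 = 5.4 people, or 0.05 × 24 = 1.2 to 0.15 × 24 = 3.6 in Part II alone. With k carriers and an assumed flare risk f each, the chance of at least one flare is 1 − (1 − f)^k:

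| k | f = 0.05 | f = 0.10 | f = 0.20 | f = 0.30 |
|---|---|---|---|---|
| 1 | 0.05 | 0.10 | 0.20 | 0.30 |
| 2 | 0.098 | 0.19 | 0.36 | 0.51 |
| 5 | 0.226 | 0.41 | 0.672 | 0.832 |

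The range is too wide to be an estimate. It shows only that the case is not remote if a few carriers are enrolled.

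**The plan's own figures (8.1.1).** 1 − 0.95^33 = 0.816, against 81.6% power stated; 1 − 0.9999^33 = 0.0033, against 0.003 stated; 33/(1 − 0.075) = 35.7, rounded up to the stated 36. All reproduce. None depends on this point, because the confirmatory rule concerns SAEs associated with the vaccine.

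**The case against.** The strongest case on the other side is that nothing important is lost.

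- **The event stays in the primary endpoint.** A flare is an AE, counted to day 56, and an SAE to the final visit if serious. This stands. A reader might infer that admitted volunteers cannot contribute an immune-mediated signal at all; the documents do not support that.
- **The DSMB sees it.** Section 9.5 gives the board solicited and unsolicited AEs, AESIs and SAEs, and 9.4.1 promises it all safety-relevant events. This stands too. What is missing is the AESI label, not the event.
- **Rapid reporting is barely affected.** Section 9.1.4 says only that communication within 48 hours can be appropriate, and 9.3.1 sends SAE reports to the sponsor within 24 hours regardless. Agreed.
- **The warning is narrow.** It speaks of the TLR ligand class and of skin disorders. It supports psoriasis; Hashimoto thyroiditis rests on the definitional gap alone. Nor is psoriasis the only listed disease that the protocol mentions as a possible effect: 5.7.2.3 reports erythema nodosum with Montanide in 2 of 36 patients, and its new onset would already be an AESI.
- **Few people are involved.** Only mild psoriasis is admitted, and Part I volunteers had to be free of clinically significant health problems and take no medication except contraception. This stands, and it makes the assumed counts for all 36 generous.
- **Separating new disease from fluctuation of known disease is defensible in an uncontrolled trial.** True, but that argues for reporting the two separately, not for leaving one out.
- **The lead-in of 9.1.4 omits the word *novel*.** It does, so the section is inconsistent and classification is left to the investigator. The plain reading of the itemised list is new-onset disease.

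**Conclusion.** The point holds as a gap in the wording of 9.1.4. It has two consequences: a flare of an admitted listed disease is left out of the pIMD line and of the AESI item in the DSMB report, and a non-serious flare first arising between day 56 and month 6 has no clear place in the primary endpoint. The effect is probably small and cannot be quantified from the documents. No test, threshold or sample-size figure depends on it.

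A reader might infer that AESI incidence would be reported as 0% when it should be 2.8%. That is not supported. Granuloma alone puts any-AESI incidence at 100% in Part I, so the 2.8% can apply only to a pIMD line, and only if one flare occurs. The conclusion assumes that *novel* means new onset and that 9.2 governs AE collection after Visit 5. If the Table 1 mark at V6-7 governs instead, late flares would be recorded but still not labelled as AESIs.

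**What to change.** Change the third AESI item in 9.1.4 to: *new onset or exacerbation of a potential immune-mediated disease listed in Appendix 14.6*, and bring the lead-in sentence into line with it. Use the medical history and physical examination already taken at screening as the reference for an admitted volunteer's disease. In the DSMB report and the final analysis, show new onset and exacerbation separately, on a pIMD line kept apart from granuloma. Reconcile 9.2 with the V6-7 entry in Table 1 so that it is clear which AEs are collected after day 56.

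The cost is a short amendment and a change to the AESI page of the eCRF. The downside is a few more AESI reports and possibly a higher pIMD incidence. Event classification changes; eligibility, dosing and sample size do not.

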9.1.5. Serious Adverse Event and Serious Adverse Reaction

AEs are classified as "non-serious" or "serious".

A serious adverse event (SAE) is one that at any dose:

- Results in death.
- Is life-threatening (the term life-threatening refers to an event in which the subject was at risk of death at the time of event and not to an event which hypothetically might have caused death if it was more severe).
- Requires subject hospitalization or prolongation of existing hospitalization.
- Results in persistent or significant disability/ incapacity.
- Causes a congenital anomaly / birth defect.
- Is medically significant (e.g. suspected transmission of an infectious agent via medicinal product). Moreover, there are other situations - such as

Protocol		
Protocol code and Short Title:	P-pVAC-SARS-CoV-2	Date/Version:08.03.2021/V1.4

important medical events that may not be immediately life threatening or result in death or hospitalization, but may jeopardize the patient or may require intervention to prevent one of the other outcomes listed above. Important medical event [ICH E2A; EMA/155528/2018]: Examples of such events are intensive treatment in an emergency room or at home for allergic bronchospasm; blood dyscrasias or convulsions that do not result in hospitalisation; development of drug dependency or drug abuse (Important medical event terms list (MedDRA \geq version 23.0).

9.2. Period of Observation

For the purpose of this trial, the period of observation for collection of AEs extends from the time of administration of the IMP until Visit 5.

All AEs that occur in the course of a clinical trial regardless of the causal relationship must be monitored and followed up until the outcome is known or no more information is achievable.

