The combination of multi-peptide vaccine with the TLR1/2 ligand XS15 emulsified in Montanide ISA 51 VG with the above described dosing was already evaluated in a healthy volunteer as well as in cancer patients (n=12). Multi-peptide vaccines included beside tumor-associated neoepitopes and self-peptides also viral T-cell epitopes derived from CMV and SARS-CoV-2. In all vaccinated individuals peptide-specific T-cell responses could be detected after one single vaccination. For viral T-cell epitopes including SARS-CoV-2 derived peptides strong T-cell responses could even be detected ex vivo without in vitro amplification of T-cells after one single vaccination. Immune responses after vaccination were shown to last for more than 1,5 years so far. Furthermore, the safety profile of these vaccines with similar composition and dosing as for the CoVac-1 vaccine was very good after a single vaccination, showing only grade 1 local reaction at vaccination side after single injection. Therefore, the first-in-man evaluation of CoVac-1 with a single vaccination seems reasonable to enable efficient induction of immune response with the lowest possible number of vaccination and side effects. Please find below a detailed description of the data from in vivo administration of peptide vaccines in similar composition in a healthy volunteer and cancer patients (for more details please refer to the IB of CoVac-1).

1.1.4. *Rationale for trial design*

This is a phase I multi-peptide vaccination study using SARS-CoV-2 HLA-DR peptides in combination with the novel TLR1/2 ligand XS15 in healthy volunteers to prove safety and immunogenicity. The primary objective is incidence and severity of AEs (\geq Grade 4) after vaccination in the observational time (until day 28). Furthermore, the trial aims to expand experience on overall safety and immunogenicity in the study cohort.

This is based on the following rationale:

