- Medical history, anamnestic evaluation of SARS-CoV-2 specific symptoms
- T-cell response, approximately 60 ml blood
- Serological response, approximately 15 ml blood

6.2.7. *Volunteer's diary/card*

Each patient included in the P-pVac-SARS-CoV-2 study will receive a volunteer's card, which states that he/she is participating in the study (Appendix 13.4). This will also include a 24h emergency contact number. Furthermore, each patient will be provided with a volunteer's diary to note their symptoms daily (Appendix 13.3)

6.2.8. *Unscheduled Visit*

Subjects may contact the investigator at any time for an unscheduled phone or on-site visit should they experience clinical symptoms or signs following injection. At all unscheduled visits, the following minimum assessment will be performed: Questions concerning the history of the present illness as well as the subject's general health and lifestyle. Findings resulting in (S)AEs

Protocol		
Protocol code and Short Title:	P-pVAC-SARS-CoV-2	Date/Version:08.03.2021/V1.4

will be documented and reported as indicated. All other symptoms/signs will be reported on the next scheduled visit on eCRF.

Upon occurrence of symptoms characteristic of SARS-CoV-2 (i. e. cough, fever (cut-off $>39^{\circ}\text{C}$), loss of taste and smell, limb pain) at any time until day 56, subjects are supposed to get in touch with the investigator. Investigator will initiate SARS-CoV-2 testing for the volunteer (nose or mouth swab followed by PCR per institutional guidelines). If the test is positive, patients should be treated per investigators discretion. Positive results must be recorded as an AESI (section 9.1.4). Negative results will be followed by a second testing $\geq 24\text{h}$ later. Only upon the second negative test, patients are considered negative, all others must be reported as positive.

If participants are positively tested for SARS-CoV-2, all accompanying symptoms and treatments (e.g. hospitalisation, ICU) are recorded

Medically attended AEs and all SAEs will be recorded, and concomitant medication or vaccination will be noted. After identifying the history of the present illness and performing corresponding exams or laboratory tests, the investigator will decide on the best course of treatment according to standard medical practice.

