8.5. Interim Analysis

The primary endpoint will be evaluated in a sequential manner after every consecutive included volunteer has reached day 28. No further formal interim efficacy analysis will be performed during the conduct of the study.

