9.3. Documentation and Reporting of Adverse Events

9.3.1. Documentation and Reporting of Adverse Events by the Investigator

The investigator must document all AEs that occur during the observation period set in this protocol on the pages provided in the case report form. Additional instructions may be provided in the investigator file and in the case report form itself. The following approach will be taken for documentation:

All AEs (whether serious or non-serious) must be documented on the “adverse event” page of the eCRF.

If the AE is serious, the investigator must complete, in addition to the “adverse event” page in the case report form, a “serious adverse event report form” at the time when the SAE is detected. The investigator will document the date when he/she or any employee was first aware of the report. The initial report must be as concise as possible, including reported terms according to “Common Terminology Criteria for Adverse Events (CTCAE)-List” (one term per event), details of the current illness and (S) AE, severity, serious criteria as well as an assessment of the causal relationship between the event and the trial medication.

SAE reports (initial and follow-up reports), even if they are incomplete, should be send within 24 hours upon receipt to representative of the Sponsor:

Fax-number: [name]

Mail: [contact]

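### SAEs and AESIs are primary endpoints to month 6, but sections 9.2 and 6.2.6 do not match that window or Table 1, and the zero-of-33 rule has no time limit

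*Supplement*

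**What the plan says.** All references are to protocol V1.4.

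**Passages that run to month 6**
- Section 2.1.1 lists among the primary endpoints "SAEs from the time of injection until the final study visit for each subject" and "Incidence of AESIs until the final study visit for each subject". The final visit is Visit 7, six months after vaccination. Unsolicited AEs run to 56 days only.
- Table 1 marks AE assessments in the follow-up column (Visits 6-7). It also marks medical history there, which its footnote 5 defines to include hospitalisations and symptoms of SARS-CoV-2 infection.

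**Passages that stop earlier**
- Section 9.2: "the period of observation for collection of AEs extends from the time of administration of the IMP until Visit 5". Visit 5 is day 56 ± 2. SAEs and AESIs are not excepted.
- Section 9.3.1: "The investigator must document all AEs that occur during the observation period set in this protocol".
- Section 6.2.6, on Visits 6-7, gives as its only clinical item "Medical history, anamnestic evaluation of SARS-CoV-2 specific symptoms". The rest is blood sampling.
- Section 6.2.8, on symptoms typical of SARS-CoV-2: "at any time until day 56, subjects are supposed to get in touch with the investigator", after which PCR testing follows. Section 9.1.4 counts only PCR-proven infection as this AESI.
- Section 1.1.4 gives the primary objective as AEs of Grade 4 or higher up to day 28.

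**Decision rule**
- Section 8.2 accepts safety if none of 33 volunteers has a critical event, meaning an SAE associated with CoVac-1. It names no period over which the 33 must be free of such events.

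**The concern.** The trial has one confirmatory question: does any related SAE occur among the evaluable volunteers? The answer depends on how long they are watched. Section 2.1.1 says six months, section 9.2 eight weeks, section 1.1.4 four weeks (with a severity threshold that 2.1.1 does not have), and the rule itself gives no period. Section 9 is the operative safety section. A site that follows 9.2 and 9.3.1 literally, with 6.2.6 as its visit checklist, has no scheduled prompt to collect an SAE that begins after day 56. A related SAE missed in this way would leave the zero-of-33 rule satisfied, so the error would run in one direction, towards accepting safety.

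The SARS-CoV-2 AESI has a similar gap. It requires PCR proof, and the described route from symptoms to PCR is limited to day 56, although the endpoint continues to month 6. Section 1.2.1 relies on this route to detect possible immune-mediated worsening of a later infection. A symptom history taken at months 3 and 6 cannot supply a PCR result that was never obtained.

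**Working it through.** **1. The plan's own figures** (section 8.1.1: n = 33, P0 = 0.0001, P1 = 0.05, one or more SAEs rejects, 7.5% dropout)
- Power: 1 − 0.95^33 = 0.816, as stated.
- Actual alpha: 1 − 0.9999^33 = 0.0033, stated as 0.003.
- Enrolment: 33 / 0.925 = 35.7, so 36, as stated.

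All three reproduce. The sample-size calculation attaches no time window to the 5%.

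**2. Share of the SAE/AESI window that lies after Visit 5**
- By the protocol's own split in section 3.1 (2 months of safety follow-up, then 4 months): 4/6 = 66.7%.
- In days, taking month 6 as day 182: (182 − 56)/182 = 69.2%.

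This is the share outside the collection period in 9.2. It is not a share shown to go unwatched.

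**3. Effect on the rule if capture really ended at day 56**

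Assumptions, neither of them in the documents: 5% is the six-month risk of a related SAE, and a share f of that risk falls before day 56. The probability of seeing at least one event in 33 is then 1 − (1 − 0.05f)^33.

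| Share of risk before day 56 | Captured risk | Power |
|---|---|---|
| 100% | 5.0% | 81.6% |
| 90% | 4.5% | 78.1% |
| 75% | 3.75% | 71.7% |
| 50% | 2.5% | 56.6% |
| Constant hazard: 1 − 0.95^(56/182) | 1.57% | 40.6% |

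If AE assessment takes place at Visits 6-7 as Table 1 shows, late events are captured and power stays at 81.6%.

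**4. Passages side by side**

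| Topic | One place | Another place |
|---|---|---|
| SAE/AESI window | 2.1.1 and Table 1: to Visit 7 | 9.2 and 9.3.1: to Visit 5 |
| Assessment at Visits 6-7 | Table 1: AE assessment marked | 6.2.6: none listed |
| Primary objective | 2.1.1: AEs, SAEs and AESIs over their own windows | 1.1.4: Grade 4 or higher, to day 28 |
| Symptom-triggered PCR | 2.1.1: AESI endpoint to month 6 | 6.2.8: described to day 56 |
| Positive SARS-CoV-2 case | 9.1.4: PCR-proven | 6.2.8: anyone without a second negative test is reported as positive |

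**The case against.** The strongest reply is that the schedule already covers the window. Table 1 has the AE assessment and the medical history at Visits 6-7. Its footnote 11 asks for events to be recorded continuously. Section 6.2.8 says that all SAEs are recorded and sets no day limit in that sentence. The second sentence of 9.2 requires AEs arising during the trial to be followed to outcome, and 9.4 provides for reporting even SUSARs that arise after a volunteer has finished follow-up. On that reading, the endpoint definition and the schedule agree, and 9.2 is a drafting slip.

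Much of this stands, and it rules out several stronger conclusions that a reader might draw:

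- *That the four months after day 56 go unobserved.* Table 1 and 6.2.8 speak against this. The passages conflict; they do not settle on non-collection.
- *That the primary endpoint is finally evaluated at day 28.* Section 8.5 does say "The primary endpoint will be evaluated in a sequential manner after every consecutive included volunteer has reached day 28", but under the interim-analysis heading. Section 8.2 adds daily eCRF alerts, and neither 8.2 nor the stopping rule in 8.6 has a day-28 cut-off.
- *That the late period is counted as event-free.* No passage says so. Section 7.4.5 concerns volunteers with incomplete follow-up and leads, after case review, to failure, success or drop-out. An unrecorded late SAE would pass the rule only if 9.2 prevailed over Table 1.
- *That section 11.2 fixes the primary analysis at day 56.* It speaks of first safety data and treats final results separately.

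The low end of the power range is also an unfavourable case. A constant hazard of related SAEs over six months after a single injection is an assumption, and the documents do not support it over an early concentration of risk.

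What does not stand is the idea that Table 1 settles the matter. It cannot tell a site which passage governs, it does not supply the PCR route after day 56, and it does not give the rule in 8.2 a window.

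**Conclusion.** The inconsistency is real and affects the primary endpoint. Sections 9.2, 9.3.1 and 6.2.6 do not match section 2.1.1 and Table 1, section 1.1.4 states a different objective, and the zero-of-33 rule lacks a period. About 67-69% of the SAE/AESI window lies outside the collection period in 9.2.

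The consequence is conditional. If 9.2 governs, a late related SAE could be missed and the rule would lean towards safety. With 5% read as a six-month risk, power would lie between 81.6% (all risk before day 56) and about 40% (constant hazard), with about 72% and 57% when 75% or 50% of the risk falls before day 56. If Table 1 governs, power is unaffected. The documents fix neither the timing of risk nor the period to which the 5% refers, so no single figure for the loss can be defended. The case for correction rests on the contradiction and on the very low cost of removing it.

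**What to change.** 1. Section 9.2: end collection of non-serious AEs at Visit 5, and of SAEs and AESIs at Visit 7. The duty in 9.3.1 then follows without further change.
2. Section 6.2.6: add the SAE/AESI assessment that Table 1 already marks for Visits 6-7.
3. Section 1.1.4: replace the sentence on the primary objective with the content of 2.1.1.
4. Section 8.2: state that the zero-of-33 rule covers related SAEs to Visit 7. In 8.5, label the day-28 looks as interim.
5. Section 6.2.8: reconcile the day-56 limit on symptom-triggered testing with the AESI window in 2.1.1, and the reporting of volunteers without a second negative test with the PCR-proven definition in 9.1.4. How these are resolved is for the sponsor and investigators.

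The cost is amendment wording. Visits 6 and 7 already take place and Table 1 already schedules the assessment. Item 5 could add a few PCR tests, depending on how the sponsor resolves it.
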